# **9.2.1.2 Analysis**

The primary efficacy analysis of PFS will include all subjects in the ITT population and will evaluate whether PFS in subjects in the 60 mg cabozantinib arm is non-inferior to subjects in the 140 mg cabozantinib arm. It will include radiographic progression (rPD) events per RECIST 1.1 as determined by the IRC and deaths. The primary efficacy analysis is event based and will be conducted when at least 150 PFS events have been observed.

The following censoring rules will be applied:

- Subjects receiving subsequent anti-cancer therapy (other than palliative bone radiation) before rPD per IRC will be censored at the date of their most recent post-randomization adequate tumor assessment prior to receipt of such therapy
- Subjects who miss two or more scheduled adequate tumor assessments before rPD or death will be censored at the date of their most recent post-randomization adequate tumor assessment prior to the missed assessments
- Subjects who have not progressed or expired as of the date of the analysis data cutoff will
  be censored at the date of their most recent post-randomization adequate tumor
  assessment prior to the data cutoff date
- Censored subjects without an appropriate post-randomization adequate tumor assessment will be censored at the date of randomization

Radiographic assessments are to continue if treatment is discontinued for reasons other than rPD, per the ITT principle such subjects will not necessarily be censored.

Sensitivity analyses with alternative definitions and censoring rules will be defined in the SAP to demonstrate the robustness of the treatment effect and explore the impact of potentially informative censoring.

The median duration of PFS and its associated confidence interval (CI) will be estimated using the Kaplan-Meier product-limit method. The hazard ratio (HR) and the associated 95% CI will be estimated using a Cox proportional- hazards model with treatment group as the independent variable and stratified by the factors that were used for randomization.

Non-inferiority will be concluded if the upper 95% CI for the HR is less than the non-inferiority margin of 1.58.

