2.6 Radiographic Tumor Assessment

Radiographic tumor measurements will be made at screening, 12 weeks after randomization, and every 12 weeks thereafter. This schedule is to continue irrespective of whether study treatment is given, interrupted, reduced or discontinued. Tumor assessments will continue (and scans submitted to the IRC) through the later of:

- 12 weeks after radiographic progression per RECIST 1.1 as determined by the investigator (i.e., one additional assessment after investigator-determined radiographic progression), or
- The date of the decision to discontinue study treatment (eg, for subjects treated beyond radiographic progression per RECIST 1.1)

However, these assessments are to be discontinued if subsequent systemic anti-cancer therapy, radiation therapy, or surgery affecting tumor lesion(s) is initiated prior to meeting these above criteria.

An IRC will evaluate all blinded scans per RECIST 1.1 for disease progression and objective response for the purpose of evaluating primary and secondary study endpoints. Subject management and treatment decisions will be based upon investigator evaluations of the scans. The roles, responsibilities, and details of the processes followed by the IRC are provided in the IRC charter.

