7.1.3 Primary Analysis

The primary efficacy analysis of PFS will include all subjects in the ITT population and will evaluate whether PFS for subjects in the 60 mg cabozantinib arm is non-inferior to PFS in subjects in the 140 mg cabozantinib arm. The primary efficacy analysis is event based and will be conducted when at least 150 PFS events have been observed.

The recorded date of radiographic progression is the date of the tumor assessment visit at which progression is declared per IRC per RECIST 1.1. If multiple scan dates are associated with a tumor assessment visit, the earliest assessment date within the set will be chosen as the progression date.

Only adequate tumor assessments (ATAs) will be considered in the determination of radiographic progression and censoring dates. For the purpose of this study, ATA is defined as one that results in a time point assignment of: response (complete or partial), stable disease/(non-

CR, non-PD), or progression. For PFS, ATA is based on soft tissue evaluation by CT/MRI.

Single missing or inadequate scheduled tumor assessments will be ignored. No values will be imputed.

The censoring rules shown in Table 3 will be applied to the primary and sensitivity analyses of PFS.

Table 3: Censoring Rules for Analyses of Progression Free Survival

Туре		PFS-A1		PFS-B1	
Analysis	Primary		Primary		
Radiographic PD per		IRC	Investigator		
Population		ITT		ITT	
Condition	Outcome	Date of Outcome	Outcome	Date of Outcome	
No post-baseline ATA	Censored	Date of randomization	Censored	Date of randomization	
Death	Event	Date of death	Event	Date of death	
Radiographic soft-tissue PD	Event	Date of PD	Event	Date of PD	
Clinical deterioration	NA	NA	NA	NA	
Any systemic non-protocol anti- cancer therapy (NPACT) received on or after randomization date	Censored	Date of last ATA on or prior to initiation of therapy	Censored	Date of last ATA on or prior to initiation of therapy	
Radiation (other than to bone)	Censored	Date of last ATA on or prior to radiation	Censored	Date of last ATA on or prior to radiation	
Surgery impacting soft tissue lesions	Censored	Date of last ATA on or prior to surgery	Censored	Date of last ATA on or prior to surgery	
≥ 2 consecutive missing scheduled ATA immediately prior to rPD or death	Censored	Date of last ATA prior to the missing assessments.	Censored	Date of last ATA prior to the missing assessments.	

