Appendix A: Date Imputation Rules

Incomplete Cancer Diagnosis Date

If year is missing (or completely missing): do not impute

If only day is missing: set to 15th of the month.

If day and month are missing: set to July 1st.

If either imputation rule above results in a diagnosis date > informed consent: set diagnosis date to the date of informed consent - 1.

Incomplete Adverse Event Onset Date

Assumption: For on-study Adverse Events.

If *year* is missing (or completely missing): set to the date of first dose.

If (year is present and month and day are missing) or (year and day are present and month is missing):

If *year* = year of first dose: set the date to the first dose date.

If year < year of first dose: set month and day to December 31st.

If year > year of first dose: set month and day to January 1st.

If *month* and *year* are present and *day* is missing:

If *year* = year of first dose, and:

If *month* = month of first dose: set *day* to day of first dose.

If *month* < month of first dose: set *day* to last day of *month*.

If month > month of first dose: set day to 1st day of month.

If year < year of first dose: set day to last day of month.

If year > year of first dose: set day to 1^{st} day of month.

For all other cases: set to date of first dose.

Incomplete Prior and Concomitant Medication*, Radiation, Surgery/Procedure Start Date

If *year* is missing (or completely missing): do not impute.

If (year is present and month and day are missing) or (year and day are present and month is missing):

Set month and day to January 1st.

If year and month are present and day is missing:

Set day to 1st day of month.

Incomplete Prior and Concomitant Medication*, Radiation, Surgery/Procedure End Date

If year is missing (or completely missing): do not impute.

If (year is present and month and day are missing) or (year and day are present and month is missing):

Set *month* and day to December 31st.

If *year* and *month* are present and *day* is missing:

Set day to last day of the month.

* Including prior and concomitant medications, transfusions and Opioid pain medication record

Incomplete Subsequent Anti-Cancer Therapy* Start Date

Assumption: Anti-Cancer therapies reported on the Subsequent Anti-Cancer Therapy CRF.

If year is missing (or completely missing): set to date of last dose of study treatment + 1

If (year is present and month and day are missing) or (year and day are present and month is missing):

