If year > year of the last dose: Set *month* and day to January 1st.

If year = year of the last dose: Set month and day to last dose date of study treatment + 1

If *year* and *month* are present and *day* is missing:

Set day to 1st day of month if the resulting imputed date is greater than date of last dose. Otherwise set the imputed date to date of last dose + 1

* Including concomitant and subsequent anti-cancer therapy, surgeries and procedures, and radiation, radionuclides & radiotracers.

Incomplete Study Treatment Start Date

Define previous sequential dosing "milestone" as the latest of previous dose stop date, previous dose hold stop date, date of first dose or randomization date. If *year* is missing (or completely missing): set to date of previous sequential dosing "milestone" + 1

If (year is present and month and day are missing) or (year and day are present and month is missing): set to January 1st

If year and month are present and day is missing: set to the first day of the month

If the imputed date is before the previous sequential dosing "milestone": set to the date of previous sequential dosing "milestone" + 1

Incomplete Study Treatment Stop Date

Define next sequential dosing "milestone" as the earliest of next dose start date, next dose hold start date, date of last dose from EOT CRF or the cutoff date.

If year is missing (or completely missing): set to date of next sequential dosing "milestone" - 1

If (year is present and month and day are missing) or (year and day are present and month is missing): set to December 31st

If year and month are present and day is missing: set to the last day of the month

If the imputed date is after the next sequential dosing "milestone": set to the date of next sequential dosing "milestone" -1

Incomplete Death Date

Identify date of last known alive (LA) prior to death from the following:

- 1. Date of decision to discontinue study treatment from End of Treatment CRF
- 2. Date of last radiographic assessment from End of Radiographic Follow Up CRF
- 3. Date last known alive from Survival Follow Up CRF
- 4. Date of last lab assessment from the Labs dataset

If year is missing (or completely missing): set to date of LA + 1

If only day is missing: set to the maximum of the first of month or LA + 1

If month and day are missing:

If year of LA = year of death

Set death date to date of LA + 1

If year of most-recent contact < year of death

Set month and day to Jan 1st

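### The Appendix A rule for partial anti-cancer therapy start dates can override the recorded month, clashes with a second rule, and can reverse the order of therapy and a same-month progression

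*SAP*

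**What the plan says.** SAP Appendix A has a rule for incomplete subsequent anti-cancer therapy start dates. It opens by assuming that the record is on the Subsequent Anti-Cancer Therapy CRF.

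- Day missing: "Set day to 1st day of month if the resulting imputed date is greater than date of last dose". When that first of the month is not later than last dose, a fallback applies: "Otherwise set the imputed date to date of last dose + 1".
- Month and day missing: "If year > year of the last dose: Set *month* and day to January 1st". If the year is that of the last dose, the start is last dose + 1. An earlier year has no rule.
- Year or whole date missing: "If year is missing (or completely missing): set to date of last dose of study treatment + 1".

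The footnote sets the scope: "Including concomitant and subsequent anti-cancer therapy, surgeries and procedures, and radiation, radionuclides & radiotracers".

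A separate Appendix A rule covers start dates of prior and concomitant medication, radiation and surgery. With only the day missing, it uses the first of the recorded month and makes no reference to last dose.

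In SAP 7.1.3, Table 3, systemic therapy, non-bone radiation and soft-tissue surgery censor PFS-A1, B1 and A3 at the last adequate tumor assessment (ATA) on or before the intervention. For systemic therapy the wording is "Date of last ATA on or prior to initiation of therapy". In PFS-A2 the same interventions are events on their own date. Protocol 9.2.1.2 makes order decisive: "Subjects receiving subsequent anti-cancer therapy (other than palliative bone radiation) before rPD per IRC will be censored".

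**The concern.** A therapy start date has two uses in the PFS analyses. It decides whether a progression counts as an event, and it fixes the date of the censoring or, in PFS-A2, of the event. The imputation rule looks only at the last dose. It does not keep the result inside the month the site recorded, and it does not look at the scan dates.

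Two errors in opposite directions follow. On-treatment radiation or surgery can be dated long after it happened. Therapy that followed a progression can be dated before it. In addition, a partial date for on-study radiation or surgery can receive two different values under two rules in the same appendix, with no stated precedence beyond the CRF assumption.

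**Working it through.** **Background figure.** The planned event count reproduces and is not in dispute. The margin is exp[ln(1/0.40)/2] = 1.581. With one-sided alpha 0.025, 80% power, 1:1 allocation and a true HR of 1 (assumed; the SAP does not state it), Schoenfeld's formula 4(1.960 + 0.842)²/(ln 1.58)² gives 150.05, against 150 planned.

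**Set-up for worked dates (invented).** Randomization is on 10 Sep 2016. SAP 2.6 gives the schedule: "Radiographic tumor measurements will be made at screening, 12 weeks after randomization, and every 12 weeks thereafter". ATAs therefore fall on 3 Dec 2016, 25 Feb, 20 May and 12 Aug 2017, 84 days apart. PFS in months = (date − randomization + 1)/30.4375 (SAP 7.1.1).

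**Late dating.** Non-bone radiation is given on 15 Mar 2017 and recorded as March 2017. The last dose is on 20 Aug 2017. The first of March is not after last dose, so the imputed start is 21 Aug 2017, five months outside the recorded month. The concomitant rule would give 1 Mar 2017.

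| Case | With true date | With imputed 21 Aug |
|---|---|---|
| PFS-A2, no later scans | event 15 Mar: 187/30.4375 = 6.14 | event 21 Aug: 346/30.4375 = 11.37 |
| PFS-A1, scans stopped at radiation | censored 25 Feb: 169/30.4375 = 5.55 | censored 25 Feb: 5.55 (no change) |
| PFS-A1, scans continued, PD on 12 Aug | censored 25 Feb: 5.55 | event 12 Aug: 337/30.4375 = 11.07 |
| PFS-A1, scans continued, no PD | censored 25 Feb: 5.55 | censored 12 Aug: 11.07 (168 days late) |

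PFS-A2 is misdated directly. PFS-A1 moves only in the rows where scans continued after radiation.

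A smaller version of the same fault: therapy recorded as May 2017 with last dose on 31 May 2017 is dated 1 June.

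**Early dating.** The last dose is on 3 Jul 2017, PD is on the 12 Aug scan, and therapy starts on 22 Aug, recorded as August 2017. The imputed start is 1 Aug, before the PD.

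- PFS-A1: the event at 11.07 months becomes a censoring on 20 May, 253/30.4375 = 8.31 months, 84 days earlier.
- PFS-A2: still an event, moved from 12 Aug (11.07) to 1 Aug, 326/30.4375 = 10.71.

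**How often, given such a record.** Take a subject off drug before the month in question, with the day missing and therapy truly starting g days after PD. The event is lost if both dates share a month and PD is not on the first. With PD dates uniform, the chance is about 1 − (g + 1)/30.4375. A simulation over calendar dates agrees.

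| g (days) | Formula | Simulated |
|---|---|---|
| 3 | 0.869 | 0.868 |
| 7 | 0.737 | 0.737 |
| 14 | 0.507 | 0.507 |
| 21 | 0.277 | 0.279 |
| 28 | 0.047 | 0.050 |

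**Effect on power, for scale only.** If 5, 10 or 15 of 150 events were lost and never replaced, power would be 78.6%, 77.2% or 75.7%. The analysis waits for at least 150 events, so delay and possible bias are likelier than lost power.

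**The case against.** **The rule is limited to the Subsequent Anti-Cancer Therapy CRF, where a floor of last dose + 1 is sensible, and on-treatment radiation has its own rule.** This is fair for post-treatment records, and the CRF is not available to check. But the footnote expressly includes concomitant therapy, radiation and surgery, no precedence is stated, and the fallback has no month check.

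**Late dating hardly touches the primary analysis.** This stands. A reader might infer that the primary censoring date moves by the whole remaining time on treatment. The documents do not support that: Table 3 censors at the last ATA, not at the therapy date, and Protocol 5.5.6.1 and SAP 2.6 stop study scans once such therapy begins. The case is also narrow. Protocol 3.5.3 lists the need for systemic therapy, and local therapy given to retard progression, as reasons to stop study drug. Radiation to bone does not censor.

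**Not every sensitivity analysis inherits the error in the same way.** This also stands. A reader might assume that they all censor on these dates, but PFS-A2 counts the intervention as an event. PFS-A2 therefore keeps an event in the early case, though on the imputed date. PFS-A3 treats these interventions as PFS-A1 does, and no analysis varies the imputed date.

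**The link to PFS is inferred.** Correct. SAP 4.6 ties therapy-date imputation to medication tables. SAP 4.4 is general, and no other rule for these dates exists, so the inference is strong but remains an inference.

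**First-of-month is neutral, and ordering therapy after the scan uses outcome data.** This stands as a limit on the remedy. A same-month study scan is evidence that therapy had not begun, because scans should stop at that point. Deviations occur, however, and resolving every conflict toward an event is debatable as the only rule. Treatment is blinded, no difference between arms is shown, and SAP 11 provides for a data review before lock.

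**Conclusion.** This is a minor but real defect in the wording of Appendix A. The rule can contradict the recorded month, and two rules overlap for on-study radiation and surgery. If these dates feed Table 3, as seems intended, there are two effects:

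- Late dating misdates the PFS-A2 event. It changes PFS-A1, B1 and A3 only where scans continued after local therapy contrary to the protocol.
- Early dating can turn a PFS-A1 event into a censoring at the previous scan. It needs the last dose to precede both the imputed start and the PD scan. For subjects still on drug at PD, the imputed start falls after PD and the event is kept.

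The 74% to 28% range rests on assumed gaps of 7 to 21 days and uniform dates, and is conditional on such a record existing. A reader might instead use the plain same-month chance, 1 − g/30.4375 (77% and 31%). That is slightly too high, because a PD scan on the first is not preceded by the imputed start.

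The documents do not give the number of partial dates. It is probably small, and neither the size nor the direction of any bias in the hazard ratio can be stated.

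**What to change.** Amend SAP Appendix A before unblinding:

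1. Confine every imputed start to the recorded month and year. Where this conflicts with last dose + 1, the recorded period wins.
2. Apply the last dose + 1 floor only within that range, and only to therapies reported as post-treatment.
3. State that on-study radiation and surgery follow the first-of-recorded-month rule, and take them out of the footnote.
4. Add a rule for year-only dates earlier than the year of last dose.
5. State that these rules apply to Table 3.
6. Add a sensitivity analysis of PFS-A1 that sets each partial date to its earliest and then its latest possible value within the recorded period, including a version that orders therapy after a same-month study scan. The ordering belongs here, not as the sole primary rule, because it uses outcome data.

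The cost is appendix wording and minor programming. No extra data collection is needed. A blinded count of partial dates would show whether item 6 matters.

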Appendix B: Rounding Rules for Reported Percentages

For percentages $\geq 10\%$:

- Values \geq X.5 or above round to X+1.
- Values > X but < X.5 round to X.

For percentages < 10%:

- Values \geq X.Y5 or above round to X.Y+1.
- Values > X.Y but < X.Y5 round to X.Y.

Appendix C: Imputation Rules for Laboratory Values Outside of Quantification Range

- Laboratory values below the lower level of quantification (Q) that are reported as "< Q" or "≤ Q" in the database will be imputed by Q x 0.99 for analysis purposes. However the original value will be maintained.
- Laboratory values above the upper level of quantification (Q) that are reported as "> Q" or "≥ Q" in the database will be imputed by Q x 1.01 for analysis purposes. However the original value will be maintained.

Appendix D: Dose Modification Summary Definition and Algorithms

Define the following dose modification milestones:

A	Date dose first reduced due to AE	First date a dose was given that was > 0 and < assigned dose, due to AE
В	Date dose reduced again due to AE	First date a dose was given that was > 0 and < the level given at
		first reduction (A above), due to AE
С	Date dose first held due to AE	First date a dose record of 0 was entered, due to AE

Algorithms for selected summary items:

Template	Summary item	Algorithm
T_DOSERED	Time to first dose reduction due	Time from first dose to (A) above
	to AE	
T_DOSERED	Time to second dose reduction	Time from first dose to (B) above
	due to AE	
T_DOSEMOD	# of subjects with any	# of subjects with any of A or C (Counting unique
	modification due to AE	subjects: B is a subset of A)
T_DOSEMOD	# of unique dose level	Range of 0-3, counting incidence of A, B and C per
	modifications due to AE per	subject
	subject	
T_DOSEMOD	Time to first dose modification	Time from first dose to earliest of A or C (among those
	due to AE	with either A or C)
T_DOSEMOD	Time to second dose	Time from first dose to "second earliest" of A, B and C
	modification due to AE	(among those with 2 or more of A, B or C)

Notes:

- 1. For the purpose of counting the # of dose modifications and time to first and second dose modifications, only the first dose hold counts. But for dose hold summary all dose holds count.
- 2. The algorithm provided skips over dose increases and reductions back to a previously identified reduction. Also it is not possible for 2 dose holds to count as both a first and second dose modification.

Certificate Of Completion

Envelope Id: E2141CD162E744D2A06D9991B616F699

Subject: Please DocuSign: XL184-401-SAP-V2.docx

Source Envelope:

Document Pages: 49 Signatures: 5 Certificate Pages: 6 Initials: 0

AutoNav: Enabled

Envelopeld Stamping: Disabled

Time Zone: (UTC-08:00) Pacific Time (US & Canada)

Status: Completed

Envelope Originator:

PPD

PPD

IP Address: PPD

Timestamp

Sent: 03-Jun-2020 | 14:34

Viewed: 03-Jun-2020 | 18:27

Signed: 03-Jun-2020 | 18:27

Sent: 03-Jun-2020 | 14:34 Viewed: 03-Jun-2020 | 14:56 Signed: 03-Jun-2020 | 14:57

Record Tracking

Status: Original

03-Jun-2020 | 14:21

Holder: PPD Location: DocuSign

Signer Events

PPD

Exelixis, Inc. - Part 11

Security Level: Email, Account Authentication

(Required)

Signature

PPD

Signature Adoption: Pre-selected Style

Signature ID:

